#### 10.6.4 *Pharmacokinetic and Immunogenicity Analysis*

For all patients, trough and post-treatment concentrations of ISIS 681257 in plasma (as total full length oligonucleotides, including fully conjugated, partially conjugated, and unconjugated ISIS 681257) will be determined and summarized by treatment with stratification by subject immunogenicity status using descriptive statistics.

In addition, non-compartmental PK analysis of ISIS 681257 concentrations will be carried out on each individual patient data set in patients who received ISIS 681257 treatment, and the plasma disposition half-life ( $t_{1/2\lambda_z}$ ) associated with the apparent terminal elimination phase will be calculated, if appropriate, using available data at the End-of-Treatment and the post-treatment follow-up period from the equation,  $t_{1/2\lambda_z} = 0.693/\lambda_z$ , where  $\lambda_z$  is the rate constant associated with the apparent terminal elimination phase.

For patients in the PK subgroup only, non-compartmental PK analysis of ISIS 681257 will be carried out on each individual patient data set in patients who received ISIS 681257 treatment. The maximum observed drug concentration ( $C_{max}$ ) and the time taken to reach  $C_{max}$  ( $T_{max}$ ) will be obtained directly from the concentration-time data. Following single dosing (Day 1), area under the plasma concentration-time curve from time zero (pre-dose) to 24 hours after the dose ( $AUC_{0-24hr}$ ) will be calculated using the linear trapezoidal rule. Following multiple dosing,  $AUC_{0-24hr}$  and area under the plasma concentration-time curve during the time of each sampled dosing interval ( $\tau$ ) at steady-state ( $AUC_{\tau}$ ) will be calculated using the linear trapezoidal rule.

Other PK parameters, as appropriate, may be determined or calculated at the discretion of the PK scientist. Plasma PK parameters will be summarized using descriptive statistics with stratification by subject immunogenicity status. Exposure-response relationships between selected PD [e.g., Lp(a)] and PK measures (including but may not be limited to plasma trough concentrations) may be explored (including with and without stratification by IM status) in this study, or in a separate population PK analysis with all clinical studies combined.

The immunogenicity (IM) of ISIS 681257 will be assessed before, during, and after treatment with Study Drug (ISIS 681257 or placebo). The IM incidence (number) and incidence rate (percent) will be summarized at each evaluated study time point and at the patient level by treatment and dose, as the total number of and percent of evaluated patients with antibody negative, positive, and unknown status. Study patients with positive anti-ISIS 681257 antibody status may be further classified (when applicable) as

being either ‘persistent’, ‘transient’, or not determinable. Potential relationships of immunogenicity with selected efficacy, safety, and PK measures may be evaluated.

Additional details regarding the PK and immunogenicity analysis will be described in the SAP.

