**PROTOCOL SYNOPSIS *Continued***

Pharmacokinetic Evaluations
	
Plasma samples will be taken from all patients for the measurement of ISIS 681257 plasma trough levels throughout treatment and during the post-treatment follow-up period. In addition, in a subset of patients (approximately 12 patients per cohort), more frequent plasma samples will be taken following the first and Day 169 (for Cohorts A, B, and C) or Day 183 (for Cohorts D and E) dose to determine PK parameters. Plasma sample collection time points are detailed in Appendices A and C.
 
The plasma ISIS 681257 levels over time will be descriptively summarized by treatment with stratification by subject immunogenicity status. Apparent terminal elimination half-life will be calculated in patients who received ISIS 681257 treatment using a non-compartmental method, if data permitted. In addition, <math>C_{max}</math>, <math>T_{max}</math>, and AUC values will be calculated for the PK subgroup. PK parameters will be descriptively summarized by treatment with stratification by subject immunogenicity status.

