#### 2.3.4 *Clinical Experience*

Detailed information concerning the clinical studies conducted with ISIS 681257 can be found in the Investigator's Brochure. A summary of the study that has been conducted with ISIS 681257 is included below.

ISIS 681257-CS1 was a Phase 1 double-blind, placebo-controlled, dose-escalation study designed to assess the safety, tolerability, PK, and pharmacodynamics (PD) of single and multiple doses of ISIS 681257 administered subcutaneously (SC) to 45 healthy subjects with Lp(a)  $\geq$  the upper limit of normal (ULN) (30 mg/dL). Twenty one (21) subjects received 10 to 120 mg SC (10, 20, 40, 80, and 120 mg) as a single-dose, and 24 subjects received 10, 20, and 40 mg as multiple doses (6 doses in 21 days: 3 loading doses during the first week on alternate days (Days 1, 3, and 5), and then once a week for the next 3 weeks (Days 8, 15, and 22).

There were no serious adverse events (SAEs), or clinically-relevant changes in laboratory assessments and all subjects completed the treatment and post-treatment follow-up periods.

Constitutional symptoms such as fever, chills, increase in body temperature and arthralgias have been observed following parenteral administration of ASOs, primarily during the initial dosing period. Following SC administration of ISIS 681257 constitutional symptoms were observed in 4 of the 6 subjects who received a single-dose of 120 mg. The symptoms were mild in severity and resolved spontaneously with or without treatment with acetaminophen.

Fluctuations in platelet counts to below the lower limit of normal were observed in 5 study subjects on active drug and across doses. These changes were not considered adverse or clinically-significant by the Investigator and did not appear to be dose related.

Two (2) mild AEs of redness at the site of injection occurred 48 to 72 hours after administration in 1 subject who received ISIS 681257 in the 20 mg multiple-dose cohort. Both AEs resolved by the time of the subject's next visit.

Following SC administration, ISIS 681257 was absorbed rapidly into the systemic circulation, with median time to maximum plasma concentrations ( $T_{max}$ ) ranging from 1 to 4 hours. Similar  $T_{max}$  values were observed at all dose levels. Maximum observed plasma concentrations ( $C_{max}$ ) and  $AUC_{0-24hr}$  were dose-dependent over the studied SC dose range. The mean peak ( $C_{max}$ ) and total exposure ( $AUC_{0-24hr}$ )

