increased proportionally with dose at dose levels ranging from 10 to 40 mg, and greater than dose proportionally at dose levels ranging from 40 to 120 mg.

After reaching  $C_{max}$ , mean plasma concentrations of ISIS 681257 declined in a biphasic fashion over time, with an initial, relatively fast distribution phase that dominated the plasma clearance followed by a slower elimination phase. Characterization of the terminal elimination phase yielded an apparent terminal elimination half-life of approximately 3 to 4 weeks over a dose range of 10 to 120 mg (either single- or multiple-dose), and appeared to be independent of dose. This result is consistent with the slow elimination of ISIS 681257 observed from monkey tissues, and the comparatively long elimination half-lives observed for this chemical class.

Plasma trough concentrations (168 hours or 7 days from previous dose) monitored during the treatment period in the multiple-dose cohorts increased with increasing dose, consistent with expectations (based on preclinical assessments and experience with other compounds of this chemical class) that trough plasma concentrations reflect exposure in tissues. Plasma trough concentrations did not increase greatly after the loading period (Day 15), suggesting that accumulation in major tissues of distribution had approached steady-state after the loading period.

Overall, the human PK of ISIS 681257 are consistent with the expected PK for compounds within this chemical class.

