#### **2.4 Rationale for Dose and Schedule of Administration**

The Phase 1 program evaluated ISIS 681257 doses of 10 mg, 20 mg, and 40 mg given weekly that were found to be generally well-tolerated and to induce clinically-relevant reductions in Lp(a).

The range of dosing proposed for the present study will provide the equivalent drug exposure of 5 mg, 10 mg, 15 mg, and 20 mg administered weekly, and is predicted (based on modelling of PK/PD data obtained in Phase 1 study) to result in mean reductions from baseline in plasma Lp(a) ranging from approximately 60% to 85% at steady-state.

The highest dose selected for this study, 20 mg per week, is predicted to provide an approximately 85% reduction in Lp(a) at steady-state that is expected to be sufficient to bring almost all patients with hyperlipoproteinemia(a) into the normal range ( $Lp(a) \leq 30$  mg/dL).

The present study will also evaluate safety and efficacy at different dosing frequencies: every 4 weeks, every 2 weeks, and weekly. Patients with hyperlipoproteinemia(a) will require chronic treatment and thus every 2 weeks or every 4 weeks dosing regimens, if safe and well-tolerated, may provide advantages over weekly dosing in terms of convenience and compliance for patients. Dosing regimens of 20 mg every 2 weeks and 40 mg every 4 weeks will test if similar monthly exposure, at different frequencies of administration, will achieve similar safety and similar level of Lp(a) reduction since the reduction achieved by a given dose level is principally driven by total exposure, while individual dose levels and the related peak concentration ( $C_{max}$ ) may influence tolerance and safety.

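### Section 10.6.4 fixes the linear trapezoidal rule for AUC0-24hr and AUCtau on a sparsely sampled biphasic curve, which overstates both; linear-up/log-down is a cheap improvement

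*Protocol*

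**What the plan says.** Section 10.6.4 of the protocol names one integration method. For the PK subgroup, AUC0-24hr after the first dose, and AUC0-24hr and AUCtau after multiple dosing, "will be calculated using the linear trapezoidal rule". The discretion that the section gives the PK scientist concerns other parameters. Further PK detail is left to the SAP, but the rule itself is stated here.

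Section 2.3.4 describes the curve being integrated. Median time to peak is "ranging from 1 to 4 hours". The decline has "an initial, relatively fast distribution phase that dominated the plasma clearance followed by a slower elimination phase", with a terminal "half-life of approximately 3 to 4 weeks over a dose range of 10 to 120 mg". Mean peak and AUC0-24hr "increased proportionally with dose at dose levels ranging from 10 to 40 mg".

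The synopsis places the rich profiles "following the first and Day 169 (for Cohorts A, B, and C) or Day 183 (for Cohorts D and E) dose". Appendix C gives the multiple-dose times for the PK subgroup:

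- **Every 4 weeks (Cohorts A to C):** Day 169 pre-dose, 1, 2, 4 and 8 h, then 24 h, 48 h, 7 days (Day 176), 14 days (Day 183) and 28 days (Day 197).
- **Every 2 weeks (Cohort D):** Day 183 pre-dose, 1, 2, 4 and 8 h, then 24 h, 48 h and 14 days (Day 197).

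Section 2.4 explains why Cohorts B and D exist: "Dosing regimens of 20 mg every 2 weeks and 40 mg every 4 weeks will test if similar monthly exposure", given at different frequencies, achieves similar safety and a similar Lp(a) reduction.

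**The concern.** On the falling limb of a multi-exponential curve, the chord between two samples lies above the curve. The wider the gap relative to the local half-life, the larger the excess area. The 8-24 h gap follows soon after the peak in every cohort, so all AUC0-24hr and AUCtau values are affected. A second wide gap, 48 h to 14 days, exists in Cohort D only.

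What is at stake is the accuracy of the exposure figures reported under the secondary PK objective. A further issue arises if AUCtau in Cohorts B and D is set side by side, because the two cohorts are sampled differently over the interval.

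**Working it through.** The protocol states no AUC value, so there is no figure to reproduce. The check compares each rule with the exact area under curves that fit the protocol's description.

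**Inputs from the protocol:** the Appendix C times; time to peak 1 to 4 h; terminal half-life 3 to 4 weeks; biphasic decline; dose proportionality from 10 to 40 mg.

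**Assumed, not in the protocol:** distribution half-life h of 2, 3, 5, 8 or 12 h; terminal coefficient f of 0.003 or 0.01; absorption rate ka of 0.7/h, which puts the peak between about 2 and 4 h for all these h; linear kinetics.

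**Step 1, one gap by hand.** For a pure exponential over a gap Δ, with x = Δ·ln2/h, linear area over true area = (x/2)(1 + e^-x)/(1 - e^-x). For 8 to 24 h, Δ = 16:

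- h = 4: x = 2.773, ratio 1.386 × 1.0625/0.9375 = 1.57.
- h = 8: x = 1.386, ratio 0.693 × 1.25/0.75 = 1.155.
- h = 12: x = 0.924, ratio 1.07.

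If only the terminal phase remains at 48 h, the 288 h gap to 14 days is overstated by just 1.3% (3 weeks: x = 288·ln2/504 = 0.396) or 0.7% (4 weeks). That gap matters only if some of the fast phase survives to 48 h.

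**Step 2, why Cohorts B and D differ.** After a unit bolus, the fast phase still has height 2^(-48/h) at 48 h. With α = ln2/h, the linear excess over the next gap, as a share of fast-phase AUC, is about 2^(-48/h)·(α·Δ/2 - 1). Δ is 288 h in D and 120 h in B.

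- h = 5: D 0.00129 × (19.96 - 1) = 2.4%; B 0.00129 × (8.32 - 1) = 0.9%.
- h = 8: D 0.0156 × (12.48 - 1) = 17.9%; B 0.0156 × (5.20 - 1) = 6.6%.
- h = 12: D 0.0625 × (8.32 - 1) = 45.7%; B 0.0625 × (3.47 - 1) = 15.4%.

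**Step 3, full model.** C(t) = Σ A_i·ka/(ka - λ_i)·(e^(-λ_i t) - e^(-ka t)), with A = 1 - f for the fast phase and f for the terminal phase. At steady state each exponential is divided by 1 - e^(-λτ) (for the absorption term, 1 - e^(-ka·τ)). True AUCtau per unit dose is (1 - f)/α + f/β, so R = 2 × AUCtau(D)/AUCtau(B) has true value 1. Ranges cover both terminal half-lives and both f. AUC0-24hr is Day 1. Lin is the linear rule; log is linear-up/log-down on the same samples.

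| h | AUC0-24hr lin | log | B AUCtau lin | log | D AUCtau lin | log | R lin | R log |
|---|---|---|---|---|---|---|---|---|
| 2 | +19 to +20% | 0 to +4% | +5 to +12% | +1 to +2% | +5 to +12% | +2% | 1.001-1.002 | 1.005-1.009 |
| 3 | +19% | -1 to +1% | +7 to +14% | 0 to +1% | +7 to +14% | +1 to +2% | 1.001 | 1.007-1.009 |
| 5 | +12 to +13% | -2 to -1% | +7 to +13% | 0 to +1% | +8 to +15% | +2 to +3% | 1.008-1.013 | 1.012-1.017 |
| 8 | +6% | -1% | +9 to +14% | +3 to +4% | +17 to +25% | +10 to +12% | 1.065-1.096 | 1.061-1.080 |
| 12 | +3% | -1% | +14 to +20% | +5 to +7% | +35 to +49% | +23 to +24% | 1.185-1.245 | 1.152-1.173 |

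With Cohort B restricted to the time points both schedules share (through 48 h, then 14 days and end of interval), R is 0.998-1.000 under the linear rule and 1.005-1.023 under log-down, across the whole grid.

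For steady-state AUC0-24hr in Cohort D, the linear rule gives +3 to +19% and log-down -1 to +7%, the 7% arising only at h = 2.

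**Step 4, sensitivity.** A second grid of 204 combinations varied time to peak (1, 2, 4 h), h (2 to 12 h) and the fast-phase share of AUC (50 to 95%). Linear bias was always positive: Day 1 AUC0-24hr +1 to +20%, B +6 to +21%, D +6 to +53%, and R inflated by 0 to 26% (median 2%). Log-down gave -6 to +1%, -5 to +7%, -5 to +24%, and R inflated by 0.3 to 17%.

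**The case against.** The linear trapezoid is a standard non-compartmental convention. The 8-24 h gap is common to every cohort, so it favours no regimen. AUC comes from about 12 patients per cohort, is summarised descriptively, and enters neither the primary Lp(a) analysis nor the dose-selection criteria in section 10.1.4. Log-down has its own error, down to -6% in the wider grid. All of this stands and limits the importance of the point. It does not make the linear rule the better choice: its bias had the same sign in every combination and was usually larger.

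A reader might go further and infer that the linear rule biases the matched comparison of Cohorts B and D, and so undermines section 2.4. The documents do not support that, for three reasons:

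- The rule is not the cause. Changing it leaves R at 1.06 to 1.17 for h of 8 to 12 h and slightly raises R at shorter h. Equalising the time points brings R to about 1 under either rule.
- The size depends on a half-life that the protocol does not give. Its description of the distribution phase as relatively fast leans towards the short end, where the effect is negligible, but does not settle it.
- The protocol plans no AUC comparison of B with D and does not name AUCtau as the test of section 2.4. Similar monthly exposure is a premise there, supported by equal total dose and dose-proportional kinetics. The exposure measure that section 10.6.4 names for exposure-response work is the trough, which needs no integration.

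**Conclusion.** The point holds as a minor improvement to secondary, descriptive PK estimates. On the main grid, the linear rule overstates AUC0-24hr by about 3 to 20%, and AUCtau by about 5 to 20% in Cohort B and 5 to 49% in Cohort D. The direction follows from the shape of the curve; the size rests on the assumed distribution half-life of 2 to 12 h. The AUC0-24hr error is largest when distribution is fast, and the Cohort D AUCtau error when it is slow.

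The difference between B and D is a separate limitation of the sampling schedule. It is at most about 1% for a distribution half-life up to 5 h and about 7 to 25% at 8 to 12 h. It matters only if the two AUCtau values are compared.

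**What to change.** 1. In section 10.6.4, replace the linear rule with the linear-up/logarithmic-down trapezoidal rule, using actual sampling times, for AUC0-24hr and AUCtau. On the main grid this brings Day 1 AUC0-24hr to within about 4% and Cohort B AUCtau to within about 7%. Cohort D AUCtau comes within about 3% if distribution is fast, but can remain up to 24% too high if it is slow.
2. If AUCtau is compared between B and D, add a version with Cohort B computed only from the shared time points. Keep the full-sample value as B's own estimate, because at h = 12 dropping the 7-day sample raises B's own log-down bias from 5-7% to 20-21%.

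The cost is one phrase, one software setting and one extra derivation from samples already planned. Reported AUCs become smaller, by up to about 20%, and less directly comparable with any AUC computed by the linear rule. Neither change removes the residual bias in Cohort D's own AUCtau under slow distribution. That would need a sample near 7 days, as Cohort B has, and therefore an extra visit for the subgroup.

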## **11. INVESTIGATOR’S REGULATORY OBLIGATIONS**

### **11.1 Informed Consent**

The written informed consent document should be prepared in the language(s) of the potential patient population, based on an English version provided by the Sponsor or designee.

Before a patient’s participation in the trial, the Investigator is responsible for obtaining written informed consent from the patient or legally acceptable representative after adequate explanation of the aims, methods, anticipated benefits, and potential hazards of the study and before any protocol-specific screening procedures or any Study Drug ISIS 681257 or placebo) are administered.

Importantly, patients should be informed of the possibility and risks of a reduction in platelet count and other potential risks, in particular hepatic and renal risks, and the importance of strict adherence to the monitoring program. The patient or legally acceptable representative must be given sufficient time to consider whether to participate in the study.

The acquisition of informed consent and the patient’s agreement or refusal to notify his/her primary care physician should be documented in the patient’s medical records and the informed consent form should be signed and personally dated by the patient or a legally acceptable representative and by the person who conducted the informed consent discussion (not necessarily an Investigator). The original signed informed consent form should be retained in the Study Master File and in any other locations required by institutional policy, and a copy of the signed consent form should be provided to the patient or legally acceptable representative.

### **11.2 Ethical Conduct of the Study**

The Guidelines of the World Medical Association (WMA) Declaration of Helsinki dated October 2013 the applicable regulations and guidelines of current Good Clinical Practice (GCP) as well as the demands of national drug and data protection laws and other applicable regulatory requirements will be strictly followed.

### **11.3 Independent Ethics Committee (IEC)/Institutional Review Board (IRB)**

A copy of the protocol, proposed informed consent forms, other written patient information, and any proposed advertising material must be submitted to the IEC/IRB for written approval. A copy of the written approval of the protocol and informed consent form must be received by the Sponsor or designee before recruitment of patients into the study and shipment of Study Drug. A copy of the written approval of any other items/materials that must be approved by the Study Center or IEC/IRB must also be received by the Sponsor or designee before recruitment of patients into the study and shipment of Study Drug. The Investigator’s Brochure must be submitted to the IEC/IRB for acknowledgement.

The Investigator must submit to and, where necessary, obtain approval from the IEC/IRB, for all subsequent protocol amendments and changes to the informed consent document. The Investigator should also notify the IEC/IRB of SAEs occurring at the Study Center and other AE reports received from the Sponsor or designee, in accordance with local procedures.

The Investigator will be responsible for obtaining annual IEC/IRB approval/renewal throughout the duration of the study in accordance with local procedures.

#### **11.4 Patient Confidentiality**

The Investigator and Sponsor must ensure that the patient's confidentiality is maintained. On the case report forms or other documents submitted to the Sponsor or designee, patients should be identified by initials (if permitted by local law) and a patient identification number only. Documents that are not for submission to the Sponsor or designee (e.g., signed informed consent forms) should be kept in strict confidence by the Investigator.

In compliance with Federal and local regulations/ICH GCP Guidelines, it is required that the Investigator and institution permit authorized representatives of the company, of the regulatory agency(s), and the IEC/IRB direct access to review the patient's original medical records for verification of study-related procedures and data. Direct access includes examining, analyzing, verifying, and reproducing any records and reports that are important to the evaluation of the study. The Investigator is obligated to inform and obtain the consent of the patient to permit named representatives to have access to his/her study-related records without violating the confidentiality of the patient.

### **12. ADMINISTRATIVE AND LEGAL OBLIGATIONS**

#### **12.1 Protocol Amendments**

Protocol amendments must be made only with the prior approval of the Sponsor or designee. Agreement from the Investigator must be obtained for all protocol amendments and amendments to the informed consent document. The regulatory authority and IEC/IRB must be informed of all amendments and give approval for any amendments likely to affect the safety of the patients or the conduct of the trial. The Investigator must send a copy of the approval letter from the IEC/IRB to the Sponsor or designee.

